## 6. STUDY ASSESSMENTS

### 6.1. Safety Assessments

For all patients physical examination, brief neurological examination, vital signs (seated blood pressure, pulse rate, temperature, and respiration rate), clinical laboratory testing (hematology, chemistry, and urinalysis), 12-lead ECG, concomitant medication, C-SSRS, and AE assessments (including TEAEs and SAEs).

#### 6.1.1. Physical Examinations

A physical examination (evaluation of general appearance, skin, eyes, ears, nose, throat, neck, lymph nodes, chest, heart, abdomen, and extremities) will be conducted for every patient during the Visit 1 (Day 1), all monthly and quarterly visits, and Visit 7 (End of Study) or Early Withdrawal.

#### 6.1.2. Neurological Examinations

A brief neurological examination (mental status, cranial nerves, nystagmus, motor system, sensory system, reflexes, coordination, gait, and station) will be conducted for Visit 1 (Day 1), all monthly and quarterly visits, and Visit 7 (End of Study) or Early Withdrawal.

#### 6.1.3. Vital Signs

Vital signs (seated blood pressure, pulse rate, temperature and respiration rate) will be measured during Visit 1 (Day 1), all monthly & quarterly visits, and Visit 7 (End of Study) or Early Withdrawal. Additional vital sign measurements may be performed as deemed medically necessary by research personnel.

#### 6.1.4. Electrocardiograms

A resting 12-lead ECG will be conducted for every patient at Visit 1 (Day 1), all monthly & quarterly visits, and Visit 7 (End of Study) or Early Withdrawal.

#### 6.1.5. Clinical Laboratory Assessments

Blood samples for hematology and chemistry assessments and urine sample for urinalysis will be collected during Visit 1 (Day 1), all monthly & quarterly visits, and Visit 7 (End of Study) or Early Withdrawal.

- Hematology: hemoglobin, hematocrit, total and differential leukocyte count, red blood cell (RBC), and platelet count.
- Chemistry: albumin, blood urea nitrogen (BUN), creatinine, total bilirubin, alkaline phosphatase (ALP), aspartate transaminase (AST), alanine transaminase (ALT), sodium ( $Na^+$ ), potassium ( $K^+$ ), chloride ( $Cl^-$ ), lactate dehydrogenase (LDH), uric acid, glucose, and calcium.
- Urinalysis: pH, specific gravity, protein, glucose, ketones, bilirubin, blood, nitrite, leukocyte esterase, and urobilinogen. If protein, occult blood, nitrite, or leukocyte esterase values are out of range a microscopic examination will be performed.

A urine dipstick pregnancy test will be performed on all female post-menarchal patients during at Visit 1 and Visit 7 (End of Study) or Early Withdrawal.

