**Table 1: Schedule of Events**

ASSESSMENTS	SAFETY PERIOD				Early Withdrawal	TAPER PERIOD	FOLLOW-UP PERIOD i	
	Visit Number	1 a	2, 3, 4 (monthly)	5, 6 (quarterly)				
Study Time Points	Day 1	Weeks 4, 8, 12		Weeks 24, 36	End of Active Treatment (Week 48)		0-10 Days	30 Days After EOS
Visit Window (Days)	± 5	± 5		± 5	± 3			± 5
Informed consent **								
Review of inclusion/exclusion criteria **								
C-SSRS					X	X		
Review of AEDs	X	X	X		X	X		X
Review Concomitant Medications	X	X	X		X	X		X
Vital Signs b	X	X	X		X	X		
Clinical Labs c	X	X	X		X	X		
12-lead ECG	X	X	X		X	X		
Urinalysis	X	X	X		X	X		
Urine pregnancy screen for post-menarchal females	X				X	X		
Physical Examination d	X	X	X		X	X		
Brief neurological Examination e	X	X	X		X	X		
Dosing with Cannabidiol Oral Solution f	X	X	X		X f	X g		
Drug Accountability	X	X	X		X	X		X
AEs	X	X	X		X	X		X

ASSESSMENTS	SAFETY PERIOD					TAPER PERIOD	FOLLOW-UP PERIOD i
Visit Number	1 a	2, 3, 4 (monthly)	5, 6 (quarterly)	7 (End of Study)	Early Withdrawal	8	9 (Phone Call)
Study Time Points	Day 1	Weeks 4, 8, 12	Weeks 24, 36	End of Active Treatment (Week 48)		0-10 Days	30 Days After EOS
Visit Window (Days)	± 5	± 5	± 5	± 3			± 5
End of Study				X	X h		

\*\* To be completed prior to enrollment into LTS, specifically within the 2 week period that is allotted post completion of Visit 6 (End of Study) of INS011-17-103.

a For patients who enroll within the first 2 weeks after completion of Visit 6 (End of Study) of INS011-17-103 protocol.

b Vital signs will be taken after a 5-minute seated rest.

c If the total bilirubin laboratory value is abnormal, direct bilirubin will be drawn.

d The physical examination will include height, weight, and evaluation of general appearance, skin, eyes, ears, nose, throat, neck, lymph nodes, chest, heart, abdomen, and extremities.

e A brief neurological examination (mental status, cranial nerves, nystagmus, motor system, sensory system, reflexes, coordination, gait, and station) will be performed at all visits

f At-home doses will be recorded in the daily medication diary.

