### 1.4. Childhood Absence Epilepsy

Although there are currently two drugs approved for childhood absence epilepsy (CAE), valproate and ethosuximide, neither are ideal. Valproate has potentially serious side effects, including weight gain, polycystic ovary disease, liver failure, and significant teratogenic effects. Ethosuximide does not control general tonic-clonic seizures that can co-exist with CAE. In a recent study comparing ethosuximide, valproic acid, and lamotrigine, freedom from failure rates where treatment failure was defined as persistence of absence seizures at Week 16 or 20, a generalized tonic-clonic seizure at any time, excessive drug-related systemic toxicity, dose-limiting toxicity after a single downward dose modification, or withdrawal initiated by the parent

or physician, was 53% (ethosuximide), 58% (valproic acid), and 29% (lamotrigine). Therefore, there is still an unmet need for more effective anti-epileptic drugs with less side effects for these seizures. As CBD has been demonstrated to be effective in the treatment of cortical mediated epileptic encephalopathies, Insys is proposing a multiple-site, open-label, dose-finding proof of concept study of Cannabidiol Oral Solution for the treatment of refractory childhood absence epilepsy.

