**Figure 1: Study Design Schematic**

### 3.2. Patient Selection

#### 3.2.1. Inclusion Criteria

Patients must meet all of the following inclusion criteria:

1. Completed all activities through Visit 6 (End of Study) of INS011-17-103.
2. Patient and/or parent(s)/caregiver(s) fully comprehend the informed consent form (ICF) and assent form, understand all study procedures, and can communicate satisfactorily with the investigator and study coordinator, in accordance with applicable laws, regulations, and local requirements.
3. A female patient is eligible to participate in the study if she is:
  - a. Premenarchal, or
  - b. Of childbearing potential with a negative urine pregnancy test at the Screening Visit. If sexually active, she must agree to fulfill one of the following requirements:
    - i. Complete abstinence from intercourse for  $\geq$  4 weeks prior to administration of the first dose of the investigational product, throughout the Safety Period, and 4 weeks after completion or premature discontinuation from the investigational product, and agreement to use a double barrier method if she becomes sexually active.
    - ii. Use of acceptable methods of contraception throughout the study and 4 weeks after completion or premature discontinuation from investigational product. The acceptable method of contraception is double barrier method (i.e., condom plus spermicide or a condom plus intrauterine device [IUD], diaphragm, or stable hormonal contraceptive use for at least 3 months before screening and through 14 days after study completion).
4. A sexually active male patient or partner of enrolled patient must be willing to use acceptable methods of contraception throughout the study and for 4 weeks after completion of study participation or discontinuation from investigational product. The acceptable methods of birth control are abstinence or double barrier birth control (i.e., condom plus spermicide or a condom plus one of the methods listed in criterion #3).
5. In the opinion of the investigator, the parent(s)/caregiver(s) is (are) willing and able to comply with the study procedures and visit schedules, including venipuncture, and the visit schedules.

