#### 6.1.8.4. Definition of Serious Adverse Events

A serious AE (SAE) is any AE that fulfills any of the following criteria, as per 21 CFR 312.32:

- Results in death;
- Is life-threatening;
- Requires in-patient hospitalization or prolongation of existing hospitalization;
- Results in persistent or significant disability or incapacity;
- Is a congenital anomaly or birth defect;
- Is medically significant or requires intervention to prevent one of the outcomes listed above.

Serious AEs will be captured from the time of consent through the end of the study.

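### No pregnancy test is scheduled between Visit 1 and Visit 7 or Early Withdrawal, although urine is collected at every visit, and Section 6.1.8 neither makes pregnancy reportable nor follows it to outcome

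*Combined protocol and SAP*

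**What the plan says.** The parts of the protocol that set the test schedule agree. Section 6.1.5 states: "A urine dipstick pregnancy test will be performed on all female post-menarchal patients during at Visit 1 and Visit 7 (End of Study"), and the same sentence adds Early Withdrawal. The Table 1 row "Urine pregnancy screen for post-menarchal females" is marked at Visit 1, Visit 7 and Early Withdrawal only. Sections 7.1.1 and 7.2 list the test; Section 7.1.2 (Visits 2 to 6) does not.

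Urine is available at those intermediate visits. Section 6.1.5 says that a "urine sample for urinalysis will be collected during Visit 1 (Day 1), all monthly & quarterly visits", and again at Visit 7 or Early Withdrawal.

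Inclusion criterion 3 (Section 3.2.1) requires a negative urine test at entry for girls of childbearing potential. If sexually active, they must meet one of two options, abstinence or contraception; the second applies "throughout the study and 4 weeks after completion or premature discontinuation from investigational product".

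In Section 6.1.8.4 one seriousness criterion is "Is a congenital anomaly or birth defect", and "Serious AEs will be captured from the time of consent through the end of the study". Section 6.1.8.8 follows SAEs and treatment-related AEs until they resolve or stabilize. Pregnancy does not appear in the AE definition, the SAE criteria, the reporting rules or the follow-up rules of Section 6.1.8. Visit 9, the last contact, is a phone call covering AEDs, concomitant medications and AEs (Section 7.4).

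**The concern.** Safety and tolerability are the study's only objective. The protocol makes a negative test a condition of entry and carries contraception past the last dose, but schedules no test during 48 weeks of treatment. Valproic acid is exempt from the prohibited list in Section 4.7.2, and Section 1.4 attributes "significant teratogenic effects" to valproate, so some patients could be exposed to both drugs.

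Two things are at stake. A pregnancy could go without a scheduled test for longer than a full gestation. And if a pregnancy is found, nothing in Section 6.1.8 tells the site to report it or to record its outcome, so the information may be lost to the safety database.

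**Working it through.** **Inputs.** Visit 1 is taken as day 0. Visits 2 to 7 fall at Weeks 4, 8, 12, 24, 36 and 48, with windows of ±5 days (±3 at Visit 7), from Table 1. Section 3.1 gives the periods as 48±2 weeks, 10±3 days and 30±5 days. Gestation is not in the documents; I assume 266 days from conception, range 252 to 280.

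**The plan's own duration.** 336 + 10 + 30 = 376 days = 53.7 weeks. Tolerances: 14 + 3 + 5 = 22 days = 3.1 weeks. This reproduces the synopsis figure of about 54 ± 3 weeks. If the call is counted from Visit 7, the total is 336 + 30 = 366 days = 52.3 weeks, still within that range.

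**Gap between scheduled tests (completer).** 48 × 7 = 336 days. With windows: 336 − 5 − 3 = 328 to 336 + 5 + 3 = 344. All of these exceed 280 days. A conception up to day 336 − 266 = 70 could even deliver before the Visit 7 test.

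**Gap if Visits 2 to 6 were tested.** Intervals are 4, 4, 4, 12, 12 and 12 weeks. The longest is 84 days, or 84 + 5 + 5 = 94 with windows.

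**Deliveries after SAE capture closes.** The last conception day that delivers inside the window is window length minus gestation. The share of the 336 Safety Period days falling later is 1 − (that day)/336.

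| Window | Gestation | Last day inside | Share delivering after close |
|---|---|---|---|
| 366 days (Visit 7 + 30) | 266 | 100 | 70% |
| 376 days (last dose + 30, 10-day taper) | 266 | 110 | 67% |
| 378 days (54 weeks) | 266 | 112 | 67% |
| 399 days (57 weeks) | 252 | 147 | 56% |
| 357 days (51 weeks) | 280 | 77 | 77% |

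These are shares of calendar days for a patient who stays to the end, not probabilities of pregnancy. Of the 336 − 70 = 266 conception days whose pregnancies would still be undelivered at Visit 7, 336 − 112 = 224 to 336 − 100 = 236 lead to delivery after close, that is 84 to 89%.

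**After Visit 7.** Dosing can continue for up to 10 days of taper with no further test. Section 3.1.3 puts the call 30 days after Visit 7 or Early Withdrawal; the synopsis (Follow-Up Period) counts 30 days from discontinuation of study drug; Section 7.4 names both anchors. With a 10-day taper, a call 30 days after Visit 7 comes 30 − 10 = 20 days after the last dose, before the 28-day contraception period ends.

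**The case against.** The parts of the protocol that set the schedule agree with each other, so the test frequency is a design choice and not a contradiction. Contraception or abstinence is required of sexually active girls. Every visit includes a physical examination with weight and abdomen, plus AE review, and the investigator may order further tests to monitor events. The congenital anomaly criterion is part of a definition given as per federal regulation, and valproate's teratogenicity is raised to argue unmet need. Neither shows a trial-specific fetal hazard, and the risk summary in Section 1.6 lists none. The affected group could be very small or empty. All of this stands and limits how strongly the point can be put.

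It does not remove the point. Examinations and AE review may detect a pregnancy but are not a test. Section 6.1.8.8 follows only events already captured, and pregnancy is defined as neither an AE nor an SAE.

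A reader might infer that SAE capture always closes before a birth defect could be recorded. The documents do not support that: with a 266-day gestation, conceptions up to about day 100 to 112 could deliver inside the window, and an anomaly found before birth could be recorded earlier. Nor do they support saying that a pregnancy would surface only by self-report or at study end, or that a fetus could be exposed for 48 weeks. The 48 weeks is the gap between tests; fetal exposure is bounded by gestation.

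**Conclusion.** The point holds as a gap in monitoring and reporting. A post-menarchal girl who completes the study has no scheduled pregnancy test for 336 days (328 to 344 with windows). One who reaches menarche on study has none until Visit 7 or Early Withdrawal. Pregnancy is neither reportable nor followed to outcome. Conception on most Safety Period days, 67 to 70% with a 266-day gestation and 56 to 77% across the assumptions above, would lead to delivery after SAE capture closes. That includes most pregnancies found at Week 48 and not yet delivered.

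The test gap rests on Table 1 alone. The delivery shares rest on the assumed gestation, on completion of the study and on reading the end of the study as the follow-up call; if it meant Visit 7, the share would be 266/336 = 79%. The documents give a maximum of 30 patients and no split by sex or menarchal status, so the number affected cannot be computed. This is a cheap safety improvement and does not affect the validity of the planned analyses.

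**What to change.** - **Table 1, 6.1.5 and 7.1.2:** run the dipstick pregnancy test for post-menarchal girls on the urine already collected at Visits 2 to 6, and re-check menarchal status at each visit.
- **6.1.8.7 and 6.1.8.8:** make pregnancy in a patient reportable to the sponsor, and follow it to outcome after the last visit. More frequent testing alone would not extend SAE capture.
- **7.4:** add a pregnancy question to the Visit 9 call. Reconcile the timing of that call across the synopsis, 3.1.3 and 7.4, and with the 4-week contraception period in 3.2.1. A dipstick at Visit 8 would not cover those 4 weeks, since that visit falls 0 to 10 days after Visit 7.
- **Partner pregnancies:** optional, and dependent on the partner's consent.

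How CBD is handled after a positive test is for the sponsor's medical lead.

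The testing costs up to five dipsticks per post-menarchal girl (5 × 30 = 150 if every patient were one), with no new visit or sample. The further costs are some counselling and confidentiality burden with minors, a reporting form and, for any pregnancy that occurs, months of follow-up after the last visit.

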#### **6.1.6. Columbia Suicide Severity Rating Scale (C-SSRS)**

The C-SSRS is a prospective assessment tool routinely used in studies of drugs with any potential for CNS effects. It captures the occurrence, severity, and frequency of suicide-related thoughts and behaviors during the assessment period. For patients aged 7 to 17 years and if the developmental level is appropriate, the questionnaire will be completed at the end of the Safety Period (Visit 7) or Early Withdrawal. For patients who are less than 7 years or for whom the C-SSRS is inappropriate due to the patient's developmental functioning, a clinical assessment will be made following FDA guidelines.

(<https://www.fda.gov/downloads/drugs/guidances/ucm225130.pdf>).

Patients who have significant findings for suicidal ideation as assessed by the C-SSRS must be referred to the investigator for follow-up evaluation.

#### **6.1.7. Concomitant Medications**

Will be assessed at all visits.

#### **6.1.8. Adverse Events and Serious Adverse Events**

##### **6.1.8.1. Definition of Adverse Events**

An AE is defined as any untoward medical occurrence in a patient administered a pharmaceutical product during the course of a clinical investigation. An AE can therefore be any unfavorable and unintended sign, symptom, or disease temporally associated with the use of an investigational product, whether or not thought to be related to the investigational product.

Patients will be monitored throughout the study for AEs. Monitoring for treatment-emergent AEs will begin as soon as the patient is dosed. All AEs must be followed until they are resolved or stabilized, or until all attempts to determine resolution of the event are exhausted. The investigator should use their discretion in ordering additional tests as necessary to monitor the progress of such events.

An AE may be:

- A new illness, not documented in the patient's medical history;
- Worsening of a concomitant illness;
- An effect of the study medication; it could be an abnormal laboratory value, as well as a significant shift from baseline within normal range which the qualified investigator or medical qualified designate considers to be clinically important;
- A combination of two or more of these factors.

Surgical procedures themselves are not AEs. They are therapeutic measures for conditions that required surgery. The condition for which the surgery is required is an AE, if it occurs or is detected during the study period. Planned surgical measures permitted by the clinical study protocol and the conditions(s) leading to these measures are not AEs, if the condition(s) was

(were) known before the start of study treatment. In the latter case, the condition should be reported as medical history.

Absence seizures will not be considered AEs. However, new seizure types and injury resulting from a seizure will be captured as AEs.

Patients will be monitored throughout the study for AEs. All AEs must be followed until they are resolved or stabilized, or until all attempts to determine resolution of the event are exhausted. The investigator should use his/her discretion in ordering additional tests as necessary to monitor the progress of such events.

Adverse events reported prior to dose administration will be recorded as part of the patient's medical history.

Previous clinical trial experience has shown that somnolence, diarrhea, and transaminase elevations may be associated with CBD treatment. Therefore, Insy Development Company has identified these as Adverse Events of Special Interest.

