#### **6.1.8.7. Adverse Event Recording and Reporting**

Adverse events will be recorded throughout the study in the source documents and in the CRFs. The investigator will rate AEs for seriousness, intensity, causality, action taken, and outcome as described in the previous section.

Expedited reporting is required for serious unexpected adverse drug reactions. Fatal or life-threatening unexpected drug reactions must be reported by the Sponsor to regulatory agencies no more than 7 days after the Sponsor's first knowledge of the reaction; followed by as complete a report as possible within 8 additional days. Unexpected drug reactions must be reported no later than 15 days after the Sponsor's first knowledge of the reaction. In order to comply with these requirements, the investigator or delegate must inform the Sponsor immediately upon occurrence of any SAE. The site will complete the SAE Report Form as thoroughly as possible and e-mail it to Insys within 24 hours of the investigators first knowledge of the event.

Sponsor contact information is listed below:

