**6.1.8.8. Adverse Event Follow-Up**

All non-serious AEs that are not related or unlikely to be related to study treatment will be followed until the end of study participation. All SAEs or AEs that are considered as possibly, probably, or definitely related to treatment will be followed until resolution or stabilization.

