## 8. STATISTICS

### 8.1. Safety Endpoints

Changes in safety endpoints will be reported as mean/median change from baseline at relevant time points and as a listing of events that fall outside normal limits. Baseline is defined as Visit 6 of INS011-17-103.

- Incidence, type, and severity of AEs and serious adverse events (SAEs) associated with Cannabidiol Oral Solution (i.e., treatment-emergent adverse events [TEAEs]).
- Changes from baseline in vital signs, physical exam (including height and weight), ECG findings, and laboratory values (hematology, chemistry, and urinalysis).
- Changes from baseline in neurological exam.

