##### **8.4.3.1. Adverse Events**

The Medical Dictionary for Regulatory Activities (MedDRA, version 20.0 or higher) will be used to classify all AEs. Adverse event summaries will include only TEAEs, which will be summarized for each modal dose group. For each patient, the modal dose is the dose with the longest exposure during the study.

The number and percentage of patients with AEs will be displayed for each treatment group by system organ class and preferred term. Summaries of AEs by severity and relationship to the IP will also be provided. Serious AEs (SAEs) and AEs resulting in discontinuation will be summarized separately in a similar manner. Patient listings of AEs and SAEs will be produced.

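### On the literal text, a serious absence seizure without injury or a new seizure type is neither an AE nor an SAE, and the recording of worsening is left unclear

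*Combined protocol and SAP*

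**What the plan says.** Section 6.1.8.1 opens broadly: "An AE is defined as any untoward medical occurrence in a patient administered a pharmaceutical product during the course of a clinical investigation". It then lists what an AE may be, including a concomitant illness getting worse and an effect of the study drug. Later in the same section comes the exemption: "Absence seizures will not be considered AEs. However, new seizure types and injury resulting from a seizure will be captured as AEs". The two exceptions concern the type of seizure and its physical consequence. Neither mentions seriousness, frequency, duration or severity.

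Section 6.1.8.4 builds the SAE on the AE: "A serious AE (SAE) is any AE that fulfills any of the following criteria". Six criteria follow, hospitalization and medical significance among them.

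Later steps all start from an AE or SAE:
- Rating (Section 6.1.8.7): "The investigator will rate AEs for seriousness, intensity, causality, action taken, and outcome as described in the previous section".
- Notification (Section 6.1.8.7): "the investigator or delegate must inform the Sponsor immediately upon occurrence of any SAE", with the SAE form due within 24 hours of the investigator's first knowledge.
- Follow-up (Section 6.1.8.8): "All SAEs or AEs that are considered as possibly, probably, or definitely related to treatment will be followed until resolution or stabilization".
- Tables (Section 8.4.3.1): "Adverse event summaries will include only TEAEs, which will be summarized for each modal dose group". SAEs and AEs that lead to discontinuation are tabulated separately.

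**The concern.** It is ordinary practice to keep the expected seizures of the study disease out of the AE tables. The difficulty is that the exemption has no limit for seriousness and is not reconciled with the general AE definition above it.

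Safety and tolerability is the study's only objective (Section 2), and the incidence, type and severity of AEs and SAEs is the first endpoint listed (Section 8.1). A serious absence seizure handled as the text directs would generate no SAE report and no judgement on whether CBD contributed. If the patient were withdrawn because of it, the withdrawal and its reason would appear in the disposition table (Section 8.4.1.1) but not among AEs leading to discontinuation. For worsening that is not serious, reported TEAE incidence would depend partly on how each site reads the rule. An analysis rule cannot put back an event that was never recorded as an AE.

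**Working it through.** No calculation applies; the question is what the definitions include. The steps are as follows.

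1. *Exemption.* Section 6.1.8.1 removes absence seizures from AEs and restores new seizure types and injury only.
2. *SAE as a subset.* Section 6.1.8.4 requires an event to be an AE before its seriousness is considered.
3. *Combination.* An absence seizure that meets a seriousness criterion without injury or a new seizure type fails step 1, so it cannot enter at step 2. Rating, notification, follow-up and tables are then not triggered.
4. *Search for a rule that restores it.* Sections 3.1.1, 6.1 and 7.1 to 7.4 call for AE review but add no separate route for seizures, and no section expressly returns a serious absence seizure to the AE or SAE set.
5. *Worsening and absence status.* Several parts of Section 6.1.8.1 pull in different directions, as the table shows.

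| Event | Exemption sentence | Rest of Section 6.1.8.1 | Result |
|---|---|---|---|
| Absence seizure in the usual pattern, not serious | Not an AE | No competing rule intended | Excluded, reasonably |
| Absence seizure meeting a seriousness criterion, no injury, no new type | Not an AE | No express exception for seriousness | Excluded on the literal text |
| Clinically significant worsening in frequency, duration or severity | May be covered | May be an untoward occurrence, a worsening illness or a drug effect | Ambiguous |
| Absence status | May be covered | May be a new seizure type | Ambiguous |
| Injury from a seizure, or a new seizure type | Excepted | AE | Captured |
| Worsening of existing non-absence seizures | Does not apply | General definition applies | Not affected |

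6. *Other records.* Changes to AEDs and to the CBD dose go in the eCRF (Sections 3.1 and 3.4). Sites supply information on lack of efficacy and dropout (Section 5.2). Withdrawal reasons are tabulated (Section 8.4.1.1), neurological examinations are repeated (Section 6.1.2), and the sponsor reviews CRF data before lock (Section 10.3). These make it less likely that worsening goes unseen. None gives the event a seriousness or causality rating, and none triggers SAE notification.

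**The case against.** The best reply is that the exemption is deliberate, that its authors considered exceptions and wrote two, and that in practice most serious absence episodes would be reported. A child hospitalized for absence seizures will often have had a marked worsening or absence status, and the same section offers several routes by which either could be recorded. Section 6.1.8.4 also ties its definition to a federal regulation, and Section 9.1.2 binds investigators to applicable law.

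Much of this stands. The exemption for routine seizures should stay. The overlap between serious episodes and worsening means that the literal gap would often be narrowed by a sensible reading. But the reply relies on sites choosing the general definition over an explicit sentence, and the protocol does not tell them to. The cited regulation is not among the documents, so it cannot be used either way.

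Three stronger readings are tempting and are not supported:
- *That all worsening of absence seizures is shut out of the safety data.* The text does not say so; it leaves the matter open.
- *That an event rate can be drawn from the earlier long-term study.* Section 1.3 reports one early termination for an SAE of worsening seizures among 52 enrolled. The seizure type is not given and that study's AE rules are not shown, so this is no rate for absence seizures. It shows only that worsening seizures were once handled as an SAE, listed apart from a termination for lack of efficacy.
- *That the lack of a scheduled seizure count is itself the defect.* This is a safety study, and the absence of an efficacy measure says nothing about how AEs are defined. Nor does the observation that one patient in a maximum of 30 is 1/30 = 3.3 percentage points, which is true of any event.

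**Conclusion.** The point holds in two parts of different strength. On the literal text, an absence seizure that meets a seriousness criterion, with no injury and no new seizure type, is neither an AE nor an SAE, and nothing in the documents expressly brings it back. For clinically significant worsening and for absence status, the protocol is ambiguous, and sites could differ.

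The size cannot be given as a number, because the documents contain no frequency for serious or worsening absence seizures. The consequence is defined all the same: an affected event would lack notification, rating, follow-up and a place in the AE tables. The conclusion assumes that sites follow the exemption as worded; sites that read the general definition generously would lose less. It should be fixed, because the defect touches the study's only objective and the remedy is a short rewording.

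**What to change.** Reconcile Sections 6.1.8.1 and 6.1.8.4. Suggested wording:

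> Absence seizures in keeping with the patient's baseline pattern are not AEs. Any absence seizure or absence status that meets a criterion in Section 6.1.8.4 is recorded and reported as an SAE. Worsening from the baseline pattern that the investigator judges clinically significant is recorded as an AE and graded mild, moderate or severe. The study period of each such event (Safety, Taper or Follow-up) is recorded.

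For the baseline pattern, use the study's existing definition: "Baseline is defined as Visit 6 of INS011-17-103". The documents do not show whether seizure pattern was recorded at that visit. If it was not, it can be taken by history at Visit 1, which adds a small item there.

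Two details matter. The Moderate definition in Section 6.1.8.2 should not serve as the threshold for clinical significance: worsening could then never be graded mild, and permitted AED adjustments could become AEs by default. The study period is needed because the baseline visit closes a treatment study while AEs are also collected during taper and follow-up. Without it, seizures that return after CBD is reduced or stopped could not be told apart from worsening on treatment.

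The events go into the tables already planned in Section 8.4.3.1. The cost is a protocol amendment agreed between sponsor and investigators, with IRB approval (Sections 10.1 and 10.4). It also brings some reliance on investigator judgement in an open-label study and a possibly higher reported TEAE and SAE incidence.
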